7. SAFETY ASSESSMENTS

Reporting of Adverse Events and Serious Adverse Events

An **adverse event (AE)** is defined as any unfavorable and unintended diagnosis, symptom, sign, syndrome or disease which either occurs during the study, having been absent at baseline, or if present at baseline, appears to worsen. Adverse events are to be recorded regardless of their relationship to the study intervention.

A **serious adverse event (SAE)** is defined as any untoward medical occurrence that results in death, is life threatening, requires inpatient hospitalization or prolongation of existing hospitalization, results in persistent or significant disability/incapacity, or is a congenital anomaly.

[name] will conduct daily oversight of participant safety, and will meet regularly with staff to review progress and discuss any problems or concerns. Adverse events that are not deemed "serious adverse events" will be included in the annual report to the mentors, Independent Monitoring Committee (IMC), and IRB. The IMC will state that they have reviewed all AE reports in the annual report.

SAEs that are unanticipated, serious, and possibly related to the study intervention will be reported to the IMC, IRB, and NCCIH in accordance with requirements. Georgia State University defines an unanticipated event as an event that was (1) unforeseen; (2) more likely than not related to the research; and (3) either caused harm to participants or others, or placed them at increased risk of harm. Unanticipated events include any harm or injury (physical, psychological, social or economic) or other unexpected events occurring during the course of participation in a research study. As required by the GSU IRB, [name] will report a summary of each unanticipated event to the IRB using the IRB Unanticipated Event form within 7 business days.

Unexpected fatal or life-threatening SAEs related to the intervention will also be reported to the NCCIH Program Officer, mentors, and IMC within 7 days. Other serious and unexpected AEs related to the intervention will be reported to the NCCIH Program Official within 15 days. Anticipated or unrelated SAEs will be handled in a less urgent manner but will be reported to the Independent Monitors, IRB, and NCCIH. In the annual AE summary, the Independent Monitoring Committee Report will state that they have reviewed all AE reports.

8. INTERVENTION DISCONTINUATION

This study will be stopped prior to its completion if: (1) the intervention is associated with adverse effects that call into question the safety of the intervention; (2) any new information becomes available during the trial that necessitates stopping the trial; or (3) other situations occur that might warrant stopping the trial.

9. STATISTICAL CONSIDERATIONS AND DATA ANALYSES

Primary outcomes for this development and feasibility study are: 1) feasibility (e.g., attrition, engagement, participant ratings), 2) determining best practice for implementing and refining the text-messaging intervention (e.g., how many texts per day and at what times of day; which types of messages are most helpful; ways of increasing adherence; these variables will be assessed through participant feedback in the individual interview and final program evaluation questionnaire), and 3) an estimate of effect size (based on smoking cessation in iQuit Mindfully vs. MBAT).

Approximately 35% attrition will be deemed acceptable (based on 34% attrition in Vidrine et al.'s (2016) trial of mindfulness-based smoking cessation treatment). Level of engagement will be determined based on: 1) the proportion of texts that participants indicate reading (we expect that at least 75% will read most or all texts, based on Abroms et al.'s (2012) findings); and 2) responses to interactive text messages (we expect that at least 85% of participants will respond to at least one of the interactive text messages or use the CRAVE, STRESS, or SLIP keywords at least once, based on Heminger et al.'s (2016) findings). In terms of participant ratings, we will focus on ratings of helpfulness of the text messages and the extent to which participants would recommend the text messaging program to others (rated on 1-10 scales; the minimum acceptable rating is 6).

Effect sizes will be of greater importance than statistical significance, given that this is a feasibility study. Smoking abstinence will be defined as self-reported complete abstinence for 7 days that is biochemically confirmed with expired carbon monoxide <6ppm. Chi-square tests and t-tests will be used to evaluate group differences.

Individual interviews will be transcribed verbatim. Transcripts will be managed and coded using QSR International's NVivo 10 software, a qualitative software analysis program that allows researchers to associate codes with portions of text, to search within and across codes for patterns, and to construct classifications of codes reflecting relationships within the data. Data coding and analysis will follow both inductive and deductive approaches. An initial set of codes will be developed from the interview topics and the conceptual framework, with additional codes identified from concepts that emerge from the data. The objective of the data coding process will be to capture as many concepts as possible and then to examine the relationships and patterns of the concepts within and across transcripts to identify conceptual linkages or themes (Ayres, Kavanagh, & Knafl, 2003; Ryan & Bernard, 2003). Two independent coders will code the transcripts and then meet to discuss findings, resolve inconsistencies, and develop a preliminary coding scheme. Then the remaining transcripts will be independently coded (with regular meetings to refine the coding scheme as needed). This method of constant comparison will be used to identify themes within the data (Corbin & Strauss, 2008). This

approach involves comparing concepts across categories to identify links, patterns, connections, and differences.

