1. STUDY OBJECTIVES

Primary outcomes for this development and feasibility study are: 1) feasibility (e.g., attrition, engagement, participant ratings; specific definitions of these outcomes are described in section 9), 2) determining best practice for implementing and refining the text-messaging intervention (e.g., how many texts per day and at what times of day; which types of messages are most helpful; ways of increasing adherence), and 3) an estimate of effect size (based on smoking cessation in iQuit Mindfully vs. MBAT). Effect sizes will be of greater importance than statistical significance, given that this is a feasibility study. Secondary analyses will include: 1) effects of treatment conditions on average number of cigarettes smoked per day; 2) effects of treatment on weekly mindfulness practice; 3) effects of treatment on self-reported levels of mindfulness, affect, self-efficacy, coping, dependence, and withdrawal symptoms; and 4) associations between number of sessions attended, weekly mindfulness practice, and abstinence.

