3. STUDY DESIGN

In this randomized clinical trial, participants will be randomly assigned to one of two groups: Mindfulness-based Addiction Treatment (MBAT) or iQuit Mindfully (MBAT with the addition of between-session text messages).

Primary outcomes for this development and feasibility study are: 1) feasibility (e.g., attrition, engagement, participant ratings), 2) determining best practice for implementing and refining the text-messaging intervention (e.g., how many texts per day and at what times of day; which types of messages are most helpful; ways of increasing adherence), and 3) an estimate of effect size (based on smoking cessation in iQuit Mindfully vs. MBAT without text messaging).

Secondary analyses will include: 1) effects of treatment conditions on average number of cigarettes smoked per day; 2) effects of treatment on weekly mindfulness practice; 3) effects of treatment on self-reported levels of mindfulness, affect, self-efficacy, coping, dependence, and withdrawal symptoms; and 4) associations between number of sessions attended, weekly mindfulness practice, and abstinence.

Participants will include English-speaking adult smokers (ages 18-65). Recruitment will target a racially/ethnically diverse sample of individuals with relatively low income levels. Participants (projected $N = 70$) will be randomly assigned to “iQuit Mindfully” (with text messaging) or MBAT (without text messaging; see details of interventions in section 5 below). Approximately 10-15 participants will be enrolled per cohort, resulting in 6 cohorts (3 of each treatment).

The study will take place at Georgia State University in Atlanta, GA. All participants will receive in-person group treatment based on the 8-week MBAT protocol (Wetter et al., 2009) in addition to nicotine patch therapy and self-help materials. Assessments will occur at baseline, at each of the weekly in-person visits, at end of treatment, and at 1-month follow-up.

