Participants will be recruited through flyers (posted at venues including the GSU campus, local hospitals/community health centers, near MARTA and bus stops, community centers and shelters, etc.) and through print media in local newspapers and on buses and trains. The research team will stimulate recruitment by giving presentations, talking with staff, providing study information, and supplying flyers at local clinics and community organizations in Atlanta, GA. [name] and research staff will also visit primary care practices and health fairs to provide study information and enhance recruitment. Participants will also be recruited through online sources (e.g., Craigslist, listservs) and by word of mouth.

Participants (projected $N = 70$) will be randomly assigned to “iQuit Mindfully” (with text messaging) or MBAT (without text messaging). Approximately 10-15 participants will be enrolled per cohort, resulting in 6 cohorts (3 of each treatment).

Randomization. Randomization will take place at the end of the baseline session, after baseline assessments have been administered. Block randomization will be used to achieve balance in the number of assignments to each treatment group. This form of randomization can be conducted within each stratum (i.e., stratified permuted block design) in efforts to achieve both covariate balance and treatment balance (Hedden, Woolson, & Malcolm, 2006). Thus, in the present study stratified permuted block design will be used, and it will be most important to stratify on variables expected to interact with the text messaging intervention to predict smoking cessation. Given that younger adults typically send and receive more text messages than older adults, age is an important stratification factor. Data from the Pew Research Center indicate that mean number of texts sent/received per day is 87.7 among people aged 18-29; 27 texts/day among people ages 30-49; 11.4 texts/day among those aged 50-64; and 4.7 texts/day among those 65 and older. Thus, stratification will be based on ages 18-49 vs. 50-65 (this cutoff is consistent with the Pew Center data and also lines up with data

from [name] randomized controlled trial of mindfulness-based smoking cessation treatment, in which approximately 50% of participants were 49 or younger.)

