10. DATA COLLECTION AND QUALITY ASSURANCE

During this study, psychosocial assessments and biochemical confirmation of smoking will be conducted at baseline and at regular intervals. All of the materials collected are for research purposes only, and data will be kept in strict confidence. Confidentiality will be ensured by use of identification codes. All data will be identified with a randomly generated identification code unique to the participant. The master list containing participant numbers and participants' names will be kept in a locked file, accessible to study staff only. Although participants will sign informed consent documents, these forms will be kept in a separate locked file and will never be connected to the study data. No names will ever be recorded on the questionnaires, which will be stored in a locked file cabinet and available only to the research personnel. Participants' names will not be used in the recorded interviews (participants will be asked not to use their names, and the interviewer also will not use their names during recorded interviews). These interviews will be transcribed and coded with participant ID numbers, and audio files will be deleted within one year after the completion of data collection.

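### Baseline values of the continuous secondary outcomes are not used in any planned analysis; adjusting for them would probably sharpen those estimates modestly (low priority)

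*Combined protocol and SAP*

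**What the plan says.** Section 9 of the combined protocol and SAP gives the quantitative methods for comparing the arms in one sentence: "Chi-square tests and t-tests will be used to evaluate group differences". It comes directly after the definition of abstinence and is not expressly tied to the secondary outcomes.

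Sections 1 and 3 list the secondary outcomes without a method. They include cigarettes per day, weekly mindfulness practice and "effects of treatment on self-reported levels of mindfulness, affect, self-efficacy, coping, dependence, and withdrawal symptoms". Nothing says whether a comparison would use the final score or the change from baseline.

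The baseline data come before allocation. Section 4 states that "Randomization will take place at the end of the baseline session, after baseline assessments have been administered", and section 10 that "psychosocial assessments and biochemical confirmation of smoking will be conducted at baseline and at regular intervals". Section 3 adds: "Assessments will occur at baseline, at each of the weekly in-person visits, at end of treatment, and at 1-month follow-up". Section 6 describes the questionnaires within the baseline visit, but gives no schedule of instrument by visit.

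Two baseline variables do have a role, though not in an analysis. Age is used in randomization (section 4: "stratification will be based on ages 18-49 vs. 50-65"). Pre-treatment smoking rate is used for eligibility (section 4) and patch assignment (section 5).

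**The concern.** A participant's baseline score on a scale usually predicts the later score on the same scale. A t-test on final scores leaves that predictable part in the error term. A model that includes the baseline value removes it, at the cost of one or two degrees of freedom. With at most about 35 per arm, the intervals for these outcomes will be wide, and the data needed to narrow them appear to be collected already.

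What is at stake is the width of the intervals around secondary estimates, and nothing more. The feasibility criteria in section 9 (attrition, texts read, responses to texts, ratings) do not depend on it. Abstinence has no baseline variation to adjust for, because every participant smokes at entry.

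**Working it through.** **No figure in the plan to reproduce.** The documents give no power, SD, effect size or correlation, and the projected 70 has no derivation. (Six cohorts of 10–15 give 60–90, which contains 70.)

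**Inputs from the documents.**
- N = 70 (section 3), taken as 35 per arm because section 4 aims for balanced numbers.
- 35% attrition treated as acceptable (section 9): 70 × 0.65 = 45.5, taken as N = 46, or 23 per arm.
- Three therapy cohorts per arm (section 3).

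**Assumed.** Correlation r between baseline and follow-up; therapy-group ICC; outcome SD of 1; approximately normal scores; a t-test on final scores as comparator.

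**Step 1: precision, ignoring clustering.** With q covariates, the variance of the adjusted difference divided by that of the final-score difference is approximately

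V = (1 − r²)(N − 3)/(N − 3 − q).

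Take q = 1 if age stratum is balanced across arms (only the baseline value costs anything) and q = 2 if it is not. At N = 70 and r = 0.5:
- q = 1: 0.75 × 67/66 = 0.761, SE ratio 0.873.
- q = 2: 0.75 × 67/65 = 0.773, SE ratio 0.879.

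Simulation (20,000 trials per cell, lost degrees of freedom counted) gives these 95% half-widths in SD units. Each range runs from stratum balanced to not balanced.

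| r | t-test, 35/arm | Adjusted | Narrower | t-test, 23/arm | Adjusted | Narrower |
|---|---|---|---|---|---|---|
| 0.3 | 0.475 | 0.457–0.461 | 3–4% | 0.591 | 0.571–0.578 | 2–3% |
| 0.5 | 0.475 | 0.415–0.418 | 12–13% | 0.591 | 0.518–0.524 | 11–12% |
| 0.7 | 0.475 | 0.342–0.345 | 27–28% | 0.591 | 0.428–0.433 | 27–28% |

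At r = 0 the adjusted interval is wider by a factor of 1.008–1.015 (35 per arm) or 1.013–1.025 (23 per arm), that is, about 1–3%.

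**Step 2: break-even.** V = 1 at r = √(q/(N − 3)).
- N = 70: √(1/67) = 0.12 to √(2/67) = 0.17.
- N = 46: √(1/43) = 0.15 to √(2/43) = 0.22.

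Counting the lost degrees of freedom gives 0.12–0.18 and 0.16–0.22.

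**Step 3: if change scores are meant.** A change-score t-test has variance 2(1 − r) relative to the final-score test. The adjusted-to-change ratio is therefore (1 + r)/2 × (N − 3)/(N − 3 − q). With q = 2 it stays below 1 up to r = 2 × 41/43 − 1 = 0.91 at N = 46, and r = 2 × 65/67 − 1 = 0.94 at N = 70. The break-even in step 2 does not apply to this comparator.

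**Step 4: therapy-group clustering.** With three groups per arm, n per arm and group effects arising after baseline, the true SE ratio is

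√{[ICC/3 + (1 − ICC)(1 − r²)/n] / [ICC/3 + (1 − ICC)/n]}.

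For n = 35, r = 0.5 and ICC 0.02: √(0.02767/0.03467) = 0.893.

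| ICC (n = 35, r = 0.5) | SE ratio, formula | SE ratio, simulated | Coverage ignoring group: t-test | Adjusted |
|---|---|---|---|---|
| 0.02 | 0.893 | 0.902 | 92.4% | 91.4% |
| 0.05 | 0.919 | 0.924 | 88.8% | 86.9% |
| 0.10 | 0.944 | 0.944 | 82.5% | 79.5% |

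The simulated gain is 1 − 0.902 = 10% falling to 1 − 0.944 = 6%. At 23 per arm the simulated ratios are 0.897, 0.912 and 0.936. At r = 0.3 and 35 per arm they are 0.971, 0.976 and 0.983, a gain of only 2–3%.

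**The case against.** The strongest case against is that nothing here is an error. Under individual randomization the unadjusted difference is unbiased, and a simple test is a defensible choice in a 70-person pilot. That stands, and it sets the priority.

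The gains also rest on things the documents do not state: the comparator, the correlation and the ICC. That stands too, which is why ranges are shown. If section 9's sentence covers abstinence only, the secondary outcomes have no stated method at all, and specifying one is still useful.

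Four stronger readings are tempting but not supported:
- *The pilot's key estimate is compromised.* Section 9 does say "Effect sizes will be of greater importance than statistical significance, given that this is a feasibility study", but the effect size it plans is for smoking cessation. The documents plan no interval for any secondary scale.
- *Baseline values are used nowhere.* Smoking rate enters eligibility and patch assignment. Only use in an analysis is absent.
- *Adjustment yields a valid interval up to 28% narrower.* That figure ignores therapy groups. With clustering the gain shrinks, and the adjusted interval under-covers slightly more than the t-test's.
- *Dozens of scale-by-time comparisons are planned.* Section 6 lists many subscales, but no section says that each will be tested.

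Which score and time point to report, robust errors for cigarettes per day, and the form of any group-level interval are separate matters and not part of this point.

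**Conclusion.** The point holds as a low-priority precision improvement. No available section uses the baseline values of the continuous secondary outcomes in an analysis, and adjustment would probably help. The trade is favourable: a loss of 1–3% in width if the correlation is near zero, against 12–13% at 0.5 and 27–28% at 0.7 with 35 per arm and no clustering. If therapy groups matter, expect about 6–10% in standard error at r = 0.5, and do not read either individual-level interval as having 95% coverage.

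These sizes assume a final-score t-test as comparator, equal arms and roughly normal scores. Cigarettes per day, with quitters at zero, may gain more or less. The conclusion also relies on the scales being given at baseline, which sections 4, 6 and 10 indicate but do not list scale by scale.

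**What to change.** In section 9, replace the t-test for cigarettes per day, mindfulness, affect, self-efficacy, dependence and withdrawal with a linear model. Estimate the arm difference and its 95% interval from arm, age stratum (18–49 vs 50–65) and the same measure's baseline value. Label the interval as assuming no clustering unless therapy group is handled in the analysis.

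Keep the unadjusted comparison for abstinence, for weekly practice (its log covers techniques learned in treatment, so it has no natural baseline) and for coping (section 6 lists no instrument for it). Confirm in section 6 that the adjusted measures are given at baseline.

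The cost is a few sentences and two degrees of freedom. It needs no new visits or participants, and no new data if the scales are given at baseline as indicated.

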10. DATA COLLECTION AND QUALITY ASSURANCE

During this study, psychosocial assessments and biochemical confirmation of smoking will be conducted at baseline and at regular intervals. All of the materials collected are for research purposes only, and data will be kept in strict confidence. Confidentiality will be ensured by use of identification codes. All data will be identified with a randomly generated identification code unique to the participant. The master list containing participant numbers and participants' names will be kept in a locked file, accessible to study staff only. Although participants will sign informed consent documents, these forms will be kept in a separate locked file and will never be connected to the study data. No names will ever be recorded on the questionnaires, which will be stored in a locked file cabinet and available only to the research personnel. Participants' names will not be used in the recorded interviews (participants will be asked not to use their names, and the interviewer also will not use their names during recorded interviews). These interviews will be transcribed and coded with participant ID numbers, and audio files will be deleted within one year after the completion of data collection.

Questionnaire data (both in-person assessments and online surveys surrounding the quit date) will be collected using the REDCap (Research Electronic Data Capture) system available at Georgia State University. This will provide a secure way to collect and manage data, while avoiding potential issues with manual data entry. Georgia State University belongs to a consortium of institutional partners that work to maintain a software toolset and workflow methodology for electronic collection and management of research data. REDCap data collection projects rely on a study-specific data dictionary defined by the research team. REDCap also contains a Survey tool for building and managing online surveys. The research team can create and design surveys in a web browser and engage potential respondents using a variety of notification methods. Both REDCap and REDCap Survey systems provide secure, web-based applications that are flexible enough to be used for a variety of types of research, provide an intuitive interface for users to enter data and have real time validation rules (with automated data type and range checks) at the time of entry. These systems offer easy data manipulation with audit trails and reporting for monitoring, reporting, and querying patient records, and an automated export mechanism to common statistical packages (SPSS, SAS, Stata, R/S-Plus). REDCap application is securely housed in Amazon AWS and managed by the Research Solutions department at Georgia State University. All web-based information transmission is encrypted and the data is encrypted at rest. Amazon AWS's data centers are state of the art nondescript and secured facilities. Data will be downloaded from REDCap into a secure server that is managed by Georgia State University, password-protected, and available only to research personnel who have completed training in research with human subjects.

Additional safeguards will include appropriate password protection and physical security for all computer systems and physical data. Personal names will not be stored in electronic data files. Physical data will be stored in a locked file cabinet and available only to the research personnel. The master list containing participant numbers and participants' names will be kept in a separate locked file, also accessible to study staff only.

The Mobile Commons platform maintains a high level of security control for sending and receiving text messages. The Mobile Commons HIPAA and Text Messaging Security White Paper indicates: "All Mobile Commons systems that transmit or store sensitive client information are housed in a secure data center facility that maintains a high standard of physical security controls.... The Mobile Commons information security program includes comprehensive technical security measures geared towards protecting the confidentiality, integrity, and availability of sensitive client data.... Authentication controls are in place for access to all systems and applications that deal with sensitive

client data. All activity regarding access to, and transmission of, this data is logged. Sessions are configured to timeout after a period of inactivity. All sensitive data, including PHI and authentication credentials for system and application access, are transmitted via encrypted protocols (SSL or SSHv2) when traversing public or untrusted networks. Strong encryption is used for sensitive data stored on Mobile Commons systems. Multiple layers of procedures and technical controls are in place to verify the identity of any person or entity seeking access to any sensitive client information" (<https://www.mobilecommons.com/wp/wp-content/uploads/2014/07/Mobile-Commons-HIPAA-Text-Messaging-Security-White-Paper1.pdf>).

